- j. Refer to Section 8.5 and Table 2 for complete information on sample collection and time points.
- k. Skin biopsies may be performed at other visits as appropriate. All subjects enrolled will be asked to participate in the skin biopsy test and/or genetic analysis; however, the subject's participation is optional. Subjects should provide their consent to participate in skin biopsy and genetic analysis. Punch biopsy will be collected on Day 1 (Normal and Psoriatic skin) and Week 16 (psoriatic skin only).
- l. Samples must be collected before study drug administration on Day 1.
- m. Optional whole blood collection for DNA and mRNA requires separate pharmacogenetic informed consent form (ICF).
- n. On Days 1, 29, 57, and 85, all assessments should be performed prior to study treatment administration except for the postdose PK samples on Day 1 (Table 2). The specific order for performing the study procedures is as follows (applicable to all visits): First QoL questionnaires then the efficacy assessments, vital signs, physical examination, ECG, and blood sample collection.
- o. Subjects will remain in the study center for approximately 5 hours for the postdose assessments after IV administration and the 3 hours postdose assessments after the first and second SC injections and will be discharged as per the Investigator's judgment.

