### **6.4 Study Treatment Compliance**

The prescribed dosage, timing, and mode of administration may not be changed except in cases of infusion-related AEs, the study drug administration may be slowed or interrupted. Any departures from the intended regimen must be recorded in the electronic case report forms (eCRFs). Infusion start date/time and infusion end date/time will be documented in the subject's eCRF. Any infusion interruptions (stop date/time and restart date/time), changes in infusion rate, and/or incomplete dose administration will also be documented in the subject's eCRF.

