##### **9.4.5.1 Adverse Events and Serious Adverse Events**

Treatment-emergent adverse event: A TEAE is defined as:

- A new event that occurs during or after first dose of study treatment or,
- Any event present at baseline that worsens in either intensity or frequency after first dose of study treatment.

Only TEAEs will be summarized.

Adverse events will be coded using the MedDRA. Number of events and percentage will be tabulated by preferred term and system organ class. An event that occurred one or more times on treatment period for a subject will contribute 1 observation to the numerator and denominator

comprising all safety subjects exposed to ANB019. If the intensity or seriousness of the AE changes, the overall intensity or seriousness will be the maximum intensity or seriousness of the multiple occurrences. The TEAEs, AESIs, SAEs, TEAEs leading to treatment discontinuation, and TEAEs leading to withdrawal of subject will be tabulated for each treatment period.

Adverse events, AESIs, and SAEs will be listed for each subject.

Summaries over SOC, PT and listings of TEAEs, TEAEs leading to death, SAEs, potentially significant TEAEs, clinically important TEAEs, and TEAEs that led to discontinuation from the study or of the study drug will be presented. Summaries will also be presented by relatedness to the study drug and the severity of the TEAE.

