8.2. BASELINE

Unless otherwise specified, Baseline is defined as the last non-missing measurement taken prior to the Reference Start Date and time (including unscheduled assessments).

Where the last non-missing measurement and the Reference Start Date coincide, that measurement will be considered pre-Baseline unless there is conclusive evidence that the measurement was post study treatment administration.

Adverse events (AEs) and medications commencing on the Reference Start Date will be considered post-Baseline.

On Day 1 all assessments, except for the post-dose PK samples, should be taken before study treatment administration.

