19.1.1. TREATMENT EMERGENT ADVERSE EVENTS

A TEAE is defined as:

- A new event that occurs during or after first dose of study treatment, or
- Any event present at Baseline that worsens in either intensity or frequency after the first dose of study treatment.

In the case where it is not possible to define an AE as treatment emergent or not, the AE will be classified by the worst case i.e. Treatment Emergent.

The following summary tables will be provided by system order class (SOC) and preferred term (PT):

- Number of subjects with at least one TEAE
- Number of subjects with at least one serious TEAE
- Number of subjects with at least one TEAE by severity

- Number of subjects with at least one TEAE by relationship to study drug
- Number of subjects with at least one TEAE leading to permanent discontinuation of study drug
- Number of subjects with at least one TEAE leading to interruption of study drug
- Number of subjects with at least one TEAE leading to subject withdrawal from study
- Number of subjects with at least one TEAE leading to death

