APPENDIX 2. PARTIAL DATE CONVENTIONS

ALGORITHM FOR TREATMENT EMERGENT ADVERSE EVENTS

START DATE	STOP DATE	ACTION
Known	Known	If start date < study med start date, then not TEAE If start date >= study med start date, then TEAE
	Partial	If start date < study med start date, then not TEAE If start date >= study med start date, then TEAE
	Missing	If start date < study med start date, then not TEAE If start date >= study med start date, then TEAE
Partial, but known components show that it cannot be on or after study med start date	Known	Not TEAE
	Partial	Not TEAE
	Missing	Not TEAE
Partial, could be on or after study med start date	Known	If stop date < study med start date, then not TEAE If stop date >= study med start date, then TEAE
	Partial	Impute stop date as latest possible date (i.e. last day of month if day unknown or 31st December if day and month are unknown), then: If stop date < study med start date, then not TEAE

Page 40 of 43

START DATE	STOP DATE	ACTION
		If stop date >= study med start date, then TEAE
	Missing	Assumed TEAE
Missing	Known	If stop date < study med start date, then not TEAE If stop date >= study med start date, then TEAE
	Partial	Impute stop date as latest possible date (i.e. last day of month if day unknown or 31st December if day and month are unknown), then: If stop date < study med start date, then not TEAE If stop date >= study med start date, then TEAE
	Missing	Assumed TEAE

ALGORITHM FOR PRIOR/CONCOMITANT MEDICATIONS

START	STOP	ACTION
DATE	DATE	
Known	Known	If (stop date < study treatment start date), assign as prior
		If (stop date >= study treatment start date) and (start date <= end of
		treatment), assign as concomitant
		If (stop date >= study treatment start date) and (start date > end of
		treatment), assign as post treatment

START	STOP	ACTION
DATE	DATE	
	Partial	Impute stop date as latest possible date (i.e. last day of month if day unknown or 31st December if day and month are unknown), then: If (stop date < study med start date), assign as prior If (stop date >= study med start date) and (start date <= end of treatment), assign as concomitant If (stop date >= study med start date) and (start date > end of treatment), assign as post treatment
	Missing	If stop date is missing, medication can never be assumed as prior If (start date <= end of treatment), assign as concomitant If (start date > end of treatment), assign as post treatment

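### The SAP classifies every adverse event dated Day 1 as treatment-emergent by calendar date, against its own dose-anchored definition when onset is known to precede the infusion (minor)

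*SAP*

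**What the plan says.** **Definition.** SAP 19.1.1 defines the first kind of TEAE as "A new event that occurs during or after first dose of study treatment"; the second kind is a baseline event that worsens after that dose. Protocol 9.4.5.1 words it the same way. SAP 19.1.1 adds a worst-case clause: an event that cannot be classified either way counts as treatment-emergent.

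**Algorithm.** SAP Appendix 2 uses dates only. With a known start date, whatever is known of the stop date, the rule is "If start date >= study med start date, then TEAE". SAP 8.2 says the same in prose: "Adverse events (AEs) and medications commencing on the Reference Start Date will be considered post-Baseline". SAP 8.1 sets the Reference Start Date as the day of the first dose. SAP 5.4 declares no change from the protocol's analysis.

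**Day 1 timing.** Protocol 1.3, footnote n, says that on dosing days "all assessments should be performed prior to study treatment administration except for the postdose PK samples on Day 1", and SAP 8.2 repeats this for Day 1. The Schedule of Activities collects adverse events from Screening onward. Day 1 carries blood draws, an ECG and, in consenting subjects, punch biopsies of normal and psoriatic skin (footnote k). Protocol 6.4 states: "Infusion start date/time and infusion end date/time will be documented".

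**Reporting.** Under SAP 19 only TEAEs enter the summary tables. All events are listed with TEAEs flagged, and the denominator is all treated subjects.

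**Medications.** Protocol 9.4.3 and SAP 14 call a drug prior if it stopped before the first dose. SAP 14 also requires a concomitant drug to continue after Day 1. Appendix 2 assigns concomitant status when the stop date is on or after the treatment start date and the start date is no later than the end of treatment.

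**The concern.** The programmer will run Appendix 2, while the reader of the tables is given the definition in 19.1.1. If a subject faints at a pre-dose blood draw on Day 1 and the onset time is recorded, the definition excludes the event and the algorithm includes it. The worst-case clause does not cover this, because an event with a known pre-dose onset can be classified.

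At stake is a possible upward bias in the TEAE tables of a single-arm study with about 10 subjects. There is no control group in which the same procedural events would appear, and one subject visibly moves a percentage.

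**Working it through.** **Step 1: where the two rules differ.** Take a Day 1 infusion starting at 11:00 (an arbitrary time, for illustration) and apply both rules.

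| Onset | Appendix 2 (date ≥ dose date) | 19.1.1 (onset at or after dose) |
|---|---|---|
| Day before dosing | not TEAE | not TEAE |
| Day 1, 09:00 | **TEAE** | **not TEAE** |
| Day 1, 13:00 | TEAE | TEAE |
| Day 3 | TEAE | TEAE |

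The only disagreement is the Day 1 onset before the infusion. It needs a known onset time. Without one, the worst-case clause in 19.1.1 gives the same answer as Appendix 2.

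**Step 2: can such events arise?** Adverse events are collected before dosing, and Day 1 assessments precede dosing except for the post-dose PK samples (1 and 4 hours in protocol Table 2). Biopsies are optional. Their pre-dose timing is inferred from footnote n's reference to all assessments; footnote k gives no time relative to dosing, and the procedure order in footnote n does not list biopsies.

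**Step 3: size per subject.** The inputs are N of about 10 (SAP 5.2), a denominator of all treated subjects, and one count per subject per term (SAP 19). The plan states no figure to reproduce.

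- Shift in a term's incidence per affected subject: 1/N = 1/10 = 10 percentage points.
- Exact (Clopper-Pearson) 95% interval for 0/10: upper limit 1 − 0.025^(1/10) = 30.8%, so 0% to 30.8%.
- For 1/10: lower limit 1 − 0.975^(1/10) = 0.25%; upper limit, the 97.5% quantile of Beta(2, 9), = 44.5%.

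The intervals overlap heavily and SAP 19 specifies none for adverse events. They are given for scale only.

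**Step 4: how often.** The documents give no rate. Let p be the assumed chance that a subject has a Day 1 event known to start before the infusion. Expected subjects = 10p; chance of at least one = 1 − (1 − p)^10.

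| Assumed p | Expected subjects | Chance of at least one |
|---|---|---|
| 5% | 0.5 | 40% |
| 10% | 1.0 | 65% |
| 20% | 2.0 | 89% |

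Events in different subjects may fall under different terms, so these counts need not accumulate in one row.

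**Step 5: drugs stopped on Day 1.**

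| Drug stopped on Day 1 | Protocol 9.4.3 | SAP 14 | Appendix 2 |
|---|---|---|---|
| Before the infusion | prior | prior | concomitant |
| After the infusion | concomitant (ongoing at first dose) | neither category, since it does not continue after Day 1; concomitant only through the worst-case fallback | concomitant |

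Day 1 stop dates are foreseeable, because protocol Appendix 5 ties the stopping of systemic conventional drugs to the day of study drug administration.

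**The case against.** The best defence is that this is a declared convention. SAP 8.2 states it openly and Appendix 2 implements it. It is conservative: it can over-count but cannot miss a Day 1 onset after dosing. One sentence in 19.1.1 would remove the mismatch. That stands, and it is why the point is minor. It does not remove the conflict with the definition in force.

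Several stronger readings are tempting, and the documents do not support them:

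- *That all Day 1 procedures precede dosing.* Post-dose PK samples are drawn that day, so a Day 1 blood-draw event may be post-dose. The biopsies are optional and pre-dose only by inference.
- *That the recorded infusion time settles the matter.* The onset time is needed too, and neither document shows that it is collected; the eCRF is cited but not reproduced.
- *That the relatedness table is inflated.* Protocol Appendix 4 requires a causality assessment for every event, so a biopsy-site event can be rated unrelated. The SAP 19 rule counting a missing relationship as related applies only if that assessment is absent.
- *That SAP 8.2 contradicts itself by using date and time for baseline measurements but date alone for adverse events.* These are separate, explicit rules for different kinds of data.

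Also, all events are listed with TEAEs flagged, there is no formal hypothesis test, and no stopping criterion in protocol 4.5 uses a TEAE percentage.

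**Conclusion.** The inconsistency is real and narrow. Appendix 2 and SAP 8.2 depart from SAP 19.1.1 and protocol 9.4.5.1 for one class of event, and would count it as treatment-emergent against the plan's own definition. Severity is minor.

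The 10-point shift per affected subject follows from the planned sample size. The number of affected subjects rests wholly on the assumed p and could be zero. If onset time is not collected, no event can be shown to be misclassified and the remaining defect is one of wording. The documents establish a possible over-count in descriptive tables, not that one has occurred or that any decision would change. The medication conflict is of the same kind: the texts disagree on a drug stopped on Day 1 before the infusion.

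**What to change.** - **Adverse events (Appendix 2 and SAP 8.2).** For a Day 1 event with a recorded onset time, or a recorded answer on whether it began before or after the infusion, compare it with the recorded infusion start. Treat a pre-dose onset as not a TEAE unless it later worsens in intensity or frequency. Where time is unknown, keep the TEAE assignment.
- **If the date rule is preferred.** State in 19.1.1 that Day 1 events count as TEAEs by convention, and note this as a departure from protocol 9.4.5.1 in SAP 5.4.
- **Medications.** Reconcile protocol 9.4.3, SAP 14 and Appendix 2 for drugs stopped on Day 1, so that one rule applies. Where the stop time is unknown, the existing worst-case assignment to concomitant can remain.

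The cost is SAP wording, a small programming change and possibly one added eCRF item for Day 1 events. The small downside is that TEAE counts may fall slightly; affected events would still appear in the listings.
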